4. GENERAL ANALYTIC CONSIDERATIONS

4.1. Study Size and Power

A total of approximately 500 patients will be randomized using a 1:1 assignment ratio. The sample size is selected to achieve at least 80% power to detect a difference at the 0.05 level of significance (2-sided) in the proportion of patients who experience any emergency room visit or hospitalization, or death over 28 days.

This sample size is based on an assumed 3% event rate for the sargramostim arm and a 10% rate for the placebo arm (risk ratio of 0.30) in unvaccinated patients (similar to that observed for bamlanivimab BLAZE-1 study [Chen, 2021; Gottlieb, 2021; US FDA, 2021]). As discussed in protocol Section 4.6, the rate of any emergency room visits or hospitalization, or death over 28 days is expected to be very low, or near zero for vaccinated patients.

It is also assumed that the proportion of vaccinated patients will be approximately 20-25% of the study population, with enrollment of patients who have completed a COVID-19 vaccination regimen or participated in a COVID-19 vaccine clinical trial capped at approximately 100 patients; no events are expected to occur in these patients for either treatment arm. Therefore, the overall event rate (for unvaccinated and vaccinated patients combined) for the primary endpoint is expected to be 2.4% for sargramostim and 8.0% for placebo (risk ratio of 0.30) and maintains at least 80% power.

Note that completion of a COVID-19 vaccination regimen or participation in a COVID-19 vaccine clinical trial (yes, no) is one of the randomization stratification factors (protocol Section 6.2).

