4.3. Test Size, Confidence Levels, and Precision

Unless otherwise noted, reported confidence intervals will all be computed at the 95% confidence level; p-values will be assessed at the two-sided 0.05 significance level. Unless otherwise specified below, continuous variables will be summarized using number of patients, mean, standard deviation, median, minimum, maximum, and 25th and 75th percentiles as appropriate. Categorical variables will be summarized using number and percentage of patients in each category. The number of patients with missing responses (or variables) will be tabulated.

As this is a Phase 2b study, no adjustments for multiple comparisons will be made.

Unless otherwise specified, the following guidelines will be followed when displaying statistics:

- measures of central tendency and percentiles will be displayed with one decimal place more than the raw (collected) data,
- measures of variability will be displayed with two decimal places more than the raw (collected) data,
- percentages will be displayed with one decimal place, and
- p-values will be displayed to 4 decimal places and any less than 0.0001 will be displayed as “<0.0001”.

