 - a. If there are missing scores prior to first occurrence of a \geq 2-point increase in the NIAID ordinal scale, then it will be assumed for purposes of this sensitivity analysis that the patient's score would have been equal to whatever score was recorded directly after the missing score

9.2.3. Change from baseline in overall symptom score, and individual symptom scores, as measured by the symptom score questionnaire up to Day 28

Change from baseline in the overall symptom score, and individual symptom scores from baseline to Day 28 will be analyzed using a mixed model repeated measures analysis using a missing at random assumption for handling missing data. The model will contain baseline symptom score, treatment arm, day, and treatment-by-day interaction as fixed effects, along with strata for the two randomization factors, as appropriate. The primary estimand of treatment effect

will be the treatment differences and corresponding 95% CIs, with p-values. Estimates and corresponding 95% CIs at days 7 and 14 will also be generated. Numbers and percentages of patients with each score at baseline, and days 7, 14, and 28 will also be summarized for the overall score and for each symptom by treatment arm. All available data will be used in the analysis; no imputation will be done for missing data.

The overall symptom score will be calculated as a sum of individual scores from 14 questions on the questionnaire. Each response will be scored according to the FDA's Guidance on "Assessing COVID-19-Related Symptoms in Outpatient Adult and Adolescent Subjects in Clinical Trials of Drugs and Biological Products for COVID-19 Prevention or Treatment" (US FDA, 2020). The scores correspond to the responses:

Questions 1-10: None = 0, Mild = 1, Moderate = 2, Severe = 3;

Questions 11-12: Not at all = 0, 1-2 times = 1, 3-4 times = 2, 5 or more times = 3;

Questions 13-14: Same as usual = 0, Less than usual = 1, No sense = 2.

A sensitivity analysis will be conducted mirroring the analysis methods described above but using the following assumptions:

- Completely exclude from analysis any patients who are missing more than 20% of their required symptom score questionnaires, unless the days where they are missing questionnaires fall after the patient experienced hospitalization, ER visit, or death.

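### The symptom-score MMRM holds one baseline slope for all days, which can cost precision in the day-specific treatment differences; a baseline-by-day term would recover it at almost no cost

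*SAP*

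**What the plan says.** SAP Section 9.2.3 states that change from baseline in the overall and individual symptom scores to Day 28 "will be analyzed using a mixed model repeated measures analysis using a missing at random assumption for handling missing data". On the fixed effects it says: "The model will contain baseline symptom score, treatment arm, day, and treatment-by-day interaction as fixed effects". Stratification enters in the same sentence, with a qualifier: "along with strata for the two randomization factors, as appropriate". No baseline-by-day interaction is named there or elsewhere, and the sensitivity analysis in the same section mirrors this model. The treatment effect is reported as treatment differences with 95% CIs and p-values, and "Estimates and corresponding 95% CIs at days 7 and 14 will also be generated".

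On the score itself: "The overall symptom score will be calculated as a sum of individual scores from 14 questions on the questionnaire". Twelve items run from 0 to 3 and two from 0 to 2, so the total runs from 0 to 12 × 3 + 2 × 2 = 40. The section does not state the covariance structure. The SAP gives no SD, correlation, effect size or power for this score.

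**The concern.** With baseline as a main effect only, the model assumes that a one-point higher baseline score shifts the expected outcome by the same amount on every day. That is unlikely here. In the first days a patient's score is still close to baseline, so change depends little on baseline (slope near 0). For a patient who has become symptom-free, change equals minus the baseline score, so as more patients resolve the slope moves towards −1. The SAP itself anticipates resolution: Section 9.3 plans time to absence of COVID-19 symptoms and the proportions reaching it by Days 7, 14, 28 and 60.

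On days whose true slope lies far from the common one, the unexplained part of the baseline effect goes into the residual. The treatment differences on those days are then less precise than the collected data allow. What is at stake is the width of the intervals, and the power, for secondary endpoint 1c.

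**Working it through.** **The plan's only power figure.** Section 4.1 states that the primary event rate "is expected to be 2.4% for sargramostim and 8.0% for placebo (risk ratio of 0.30) and maintains at least 80% power". With 250 per arm ("A total of approximately 500 patients will be randomized using a 1:1 assignment ratio", so about 500/2) and a two-sided 0.05 level, the normal approximation for two proportions gives 80.7%. The figure reproduces, but it concerns the primary endpoint and says nothing about the symptom score.

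**Formula.** Let β_t be the true slope of change on baseline at day t, S the residual covariance across days, σ_t the residual SD at day t and σ_x the baseline SD. With an unstructured covariance and complete data, the common slope converges to

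b = (1′S⁻¹β) / (1′S⁻¹1),

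and the variance of the day-t treatment difference, relative to a model with baseline-by-day, is multiplied by

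R_t = 1 + (β_t − b)² σ_x² / σ_t².

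**Base case (every input is an assumption; none is in the SAP).** σ_x = 6; slopes −0.50, −0.75, −0.90 at Days 7, 14, 28; residual SDs 4.5, 3.5, 2.5; adjacent-visit correlation 0.5 (0.25 between Days 7 and 28). The weights on the three slopes are 0.132, 0.098 and 0.770, so b = −0.8325.

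- Day 7: 1 + 0.3325² × 36 / 20.25 = 1.196
- Day 14: 1 + 0.0825² × 36 / 12.25 = 1.020
- Day 28: 1 + 0.0675² × 36 / 6.25 = 1.026

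A simulation of 10,000 trials with 250 per arm agrees. The SE of the treatment difference, common slope against baseline-by-day, was 0.442 against 0.403 at Day 7, 0.317 against 0.314 at Day 14, and 0.227 against 0.224 at Day 28. Bias was under 0.01 point, and model SEs matched empirical SEs under both models.

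**What this means for power.** A contrast with 80% power under baseline-by-day has power Φ(2.802/√R − 1.960) under the common slope: 79% at R = 1.02, 72% at 1.20, 62% at 1.54 and 51% at 2.0.

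**Range over other assumptions, unstructured covariance throughout.**

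| Setting | Day 7 | Day 14 | Day 28 |
|---|---|---|---|
| Formula, 3 visits, base-case slopes and SDs, σ_x 5–7, correlation 0.3–0.85 | 1.12–1.54 | 1.01–1.20 | 1.00–1.07 |
| Formula, daily records, three resolution speeds, correlation 0.6–0.9 | 1.03–1.18 | 1.00–1.03 | 1.09–1.27 |
| Simulated patient-level exponential resolution, floor at 0, 3 visits | 1.16–1.90 | 0.99–1.16 | 1.00–1.37 |
| Same, about 18–20 records to Day 28 | 1.00–1.12 | 0.99–1.51 | 1.13–2.85 |
| Slopes −0.65, −0.75, −0.80 | 1.03 | 1.00 | 1.00 |
| Equal slopes | 1.00 | 1.00 | 1.00 |

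The simulated rows assume a baseline mean of 12 and SD of 6, with 250 per arm. Another set of resolution settings with 3, 20 or 27 days did not exceed 1.65 at Day 28, so the top of the fourth row depends on the assumed curve. With daily records the formula also gives 1.92–2.18 at Day 2 and 1.44–1.63 at Day 3.

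**The case against.** The strongest reply is that a main-effect baseline adjustment is a valid analysis, the endpoint is an unpowered secondary one in a Phase 2b trial, and none of the numbers comes from the SAP. All of that stands. It limits the point to an improvement in efficiency and leaves the size open.

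Section 4.6 commits to assessing model assumptions and using other methods if they fail, and Section 12.2 allows alternative methods. These are partial safeguards. Neither names this term, and adding it after results are known would invite criticism that pre-specification avoids.

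A reader might infer more than the document supports:

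- *That modelling change from baseline is the cause.* It is not. With a single baseline slope, a model for change with slope b and a model for the raw score with slope b + 1 give the same treatment difference. The slope varies with day in either form.
- *That the estimates are biased or the intervals invalid.* The simulation with complete data shows neither. Behaviour under dropout was not simulated.
- *That miscorrecting a chance baseline imbalance is a second harm.* It is the same harm. In the base case at Day 7 its variance is 0.3325² × 36 × 2/250 = 0.032, against 20.25 × 2/250 = 0.162 from the residual. The ratio, 0.196, is exactly the inflation already counted.
- *That precision is at least halved at Day 28.* That occurs only in some near-daily settings and cannot be shown from the SAP.

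**Conclusion.** The point holds as a probable, uneven loss of precision on secondary endpoint 1c. The direction rests on the listed fixed effects and on the expectation that symptoms resolve towards a floor of 0. The size rests entirely on assumed SDs, slopes, correlations and questionnaire schedule. The variance ratio is about 1.0 to 1.5 or more at Day 7 and usually small at Day 14; at Day 28 it runs from about 1.0 to above 2, and it is about 1.0 on all days if slopes barely vary. Section 9.2 refers to listings by day of record, and 9.2.3 uses a 20% threshold for missed questionnaires. Frequent records are therefore plausible, but the schedule itself is not in the SAP. The figures also assume an unstructured covariance, and another structure would change them. Only the overall score was examined; the individual items, scored 0–3 or 0–2, were not.

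**What to change.** Before unblinding, add the baseline-by-day interaction to the fixed effects in Section 9.2.3, so that the list comprises baseline score, arm, day, arm-by-day and baseline-by-day, with the strata as already planned. Apply it to the overall score and, for consistency, to the individual symptom scores. The mirrored sensitivity analysis then inherits it.

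The cost is one phrase in the SAP and one degree of freedom per additional day: two for three visits, or 27 for 28 days of records. With about 500 patients this is negligible. If the slopes turn out equal almost nothing is lost; if they differ, the precision is recovered.

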4.4. Strategy for Intercurrent Events

The treatment policy strategy will be employed for efficacy analyses. Analyses will consider all data, regardless of any intercurrent events, such as early discontinuation of therapy, any protocol deviations, or any additional treatments for COVID-19.

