- In patients with missing scores that account for 20% or less of their required symptom score questionnaires (or patients whose scores are missing due to prior hospitalization, ER visit, or death), handle as follows:
 - For any individual symptom scores that are missing because of the patient's prior death, impute the most severe possible answer.
 - If a patient has missing symptom scores during a period of hospitalization or ER visit, also impute the most severe possible answer for individual symptom scores.
 - For patients missing scores for any other reason, the higher of the two surrounding scores will be imputed for the missing individual symptom score (or scores).
 - The overall score will be calculated as the sum of individual symptom scores (reported or imputed) if possible.

Means and 95% CIs for the overall symptom score will be plotted over time from baseline through Day 28 by treatment arm (e.g., linear plot over time). Individual symptom scores will be summarized graphically using stacked bar charts at baseline and days 7, 14, and 28.

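### The only named symptom-score sensitivity analysis drops patients with more than 20% missing questionnaires depending on their post-randomisation outcome, so it cannot show robustness to missing data

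*SAP*

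**What the plan says.** In SAP Section 9.2.3, change from baseline in the symptom score "will be analyzed using a mixed model repeated measures analysis using a missing at random assumption for handling missing data". On data handling the main analysis is equally clear: "All available data will be used in the analysis; no imputation will be done for missing data".

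One sensitivity analysis is then named: "A sensitivity analysis will be conducted mirroring the analysis methods described above but using the following assumptions". Its first assumption is to "Completely exclude from analysis any patients who are missing more than 20% of their required symptom score questionnaires", with the exception "unless the days where they are missing questionnaires fall after the patient experienced hospitalization, ER visit, or death".

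For the patients who remain, three imputation rules apply:
- After death: "For any individual symptom scores that are missing because of the patient's prior death, impute the most severe possible answer".
- For scores missing during a hospital or ER stay: "also impute the most severe possible answer for individual symptom scores".
- For any other gap: the higher of the two neighbouring scores.

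The SAP gives no expected rate of missing questionnaires. It names no other symptom-score analysis that departs from missing at random. Section 12.2 only permits further robustness analyses; it does not commit to one.

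**The concern.** Take two patients who each miss the same large share of questionnaires. One had an ER visit before the missing days and stays in. The other had no event and is deleted, together with every score that patient did report. The events that decide this are the components of the primary endpoint in Section 9.1, so membership of the analysis set depends on an outcome that treatment is meant to change. The comparison is no longer between the groups as randomised.

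The deletion also falls in the wrong place. A mixed model under missing at random is least secure for patients with many gaps, because little of their own data supports the assumption. A useful sensitivity analysis keeps these patients and varies what is assumed about their unseen scores. This one removes them. If its result agreed with the main model, a reader could not tell whether missing data were harmless or whether the patients who might have shown otherwise had been taken out.

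**Working it through.** **Inputs from the SAP.** Section 4.1 gives about 500 patients at 1:1 (250 per arm) and overall rates of ER visit, hospitalisation or death of 2.4% on sargramostim and 8.0% on placebo. The scoring key in Section 9.2.3 gives a maximum of 10 × 3 + 2 × 3 + 2 × 2 = 40.

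**The plan's own figure.** The SAP states no figure for this analysis. Its planning rates do reproduce: 0.8 × 3% = 2.4% and 0.8 × 10% = 8.0%. With 250 per arm, a normal-approximation power calculation gives 0.807, in line with the stated 80% or more for the primary endpoint. These rates are used below only as event shares.

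**Assumptions.** Let m be the share of event-free patients removed by the 20% rule, and let all event patients be retained. The SAP gives no value for m, so a range is shown.

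**Step 1: who remains.** Share of event patients among those retained = e / (e + (1 − e)(1 − m)). For m = 20%:
- placebo: 0.08 / (0.08 + 0.92 × 0.8) = 0.0980
- sargramostim: 0.024 / (0.024 + 0.976 × 0.8) = 0.0298

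| m, both arms | Placebo | Sargramostim | Gap (percentage points) | Ratio to 5.60 |
|---|---|---|---|---|
| 0% | 8.00% | 2.40% | 5.60 | 1.00 |
| 10% | 8.81% | 2.66% | 6.15 | 1.10 |
| 20% | 9.80% | 2.98% | 6.82 | 1.22 |
| 30% | 11.05% | 3.39% | 7.66 | 1.37 |

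With unequal exclusion the gap can fall: 15% on sargramostim and 5% on placebo gives 5.57; 30% and 5% gives 4.99.

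**Step 2: effect on the mean score.** Set every event patient to 40. This is an upper bound for them, because the SAP imputes the worst answer only for scores missing after death or during a stay. Let retained event-free patients average 5 (assumption). Each arm mean is then 5 + 35 × event share. If excluded patients resemble the retained event-free ones, the difference (placebo minus sargramostim) is:
- no exclusion: 35 × 0.0560 = 1.96
- m = 10%: 35 × 0.0615 = 2.15, a rise of 0.19
- m = 20%: 35 × 0.0682 = 2.39, a rise of 0.43

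**Step 3: direction.** Same model, varying the exclusion, the event patients' score and the mean of the excluded patients:

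| Event rates, sarg. / placebo | Excluded, sarg. / placebo | Event score | Mean of excluded | Difference, all kept | Difference, rule applied |
|---|---|---|---|---|---|
| 2.4% / 8.0% | 10% / 20% | 40 | 5 | 1.96 | 2.50 |
| 2.4% / 8.0% | 20% / 10% | 40 | 2 | 2.27 | 2.04 |
| 2.4% / 8.0% | 10% / 20% | 10 | 10 | 0.71 | 0.36 |
| 2.4% / 8.0% | 20% / 10% | 10 | 10 | −0.24 | 0.29 |
| 5% / 5% | 20% / 20% | 40 | 5 | 0 | 0 |
| 5% / 5% | 10% / 20% | 40 | 5 | 0 | 0.23 |
| 5% / 5% | 20% / 10% | 40 | 5 | 0 | −0.23 |

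The rule can enlarge, shrink, create or reverse a difference. The result depends on quantities the SAP does not state.

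**The case against.** The strongest defence is one of scope. This is a single sensitivity analysis of a secondary endpoint in a Phase 2b trial. The main mixed model uses all available data and has no 20% cut. Taking the higher neighbouring score becomes unreliable when gaps are many, so a cap has a rationale. That limits what is at stake. It does not justify lifting the cap for some patients because of an outcome, or discarding scores that were reported.

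Several stronger readings are tempting, and the SAP does not support them:

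- **That the rule inflates a treatment benefit.** This needs fewer events on sargramostim and similar exclusion of event-free patients in both arms. With equal event rates and equal exclusion there is no bias, and the last table shows movement both ways.
- **That 9.8% and 3.0% are the shares of patients given the worst score.** They are event shares. A patient with a short ER visit who completes later forms keeps the reported answers.
- **That any patient with an event is exempt.** The exception covers only missing days after the event; earlier gaps are not clearly protected.
- **That the rule contradicts the FAS or the treatment-policy strategy.** Section 9.2 applies the FAS unless otherwise specified, and this analysis specifies otherwise. Section 4.4 says "Analyses will consider all data, regardless of any intercurrent events", but a skipped questionnaire is a missing-data matter, which Section 4.5 leaves to each endpoint. Discarding reported scores sits uneasily with Section 4.4, but the point does not need a contradiction.
- **That excluding 20% widens standard errors by 12%.** The factor 1/√0.8 = 1.12 treats each excluded patient as carrying full information; they have sparse data, so the loss is smaller.

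One might also say the SAP never states that this analysis is meant to test missing at random. Yet it is the only named symptom analysis that varies the handling of missing scores, so readers will use it for that.

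**Conclusion.** The point holds as a flaw in one sensitivity analysis. Membership depends on post-randomisation outcome, and the patients most relevant to the missing-data question are removed, so agreement with the main model would not show robustness. That conclusion needs no assumption about missingness rates.

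The size does need assumptions. At the SAP's planning rates, with 10-20% of event-free patients excluded equally in both arms, the gap in event share grows from 5.6 to 6.2-6.8 percentage points. With event patients set to the maximum and event-free patients averaging 5, the mean difference grows by about 0.2-0.4 points out of 40. That range belongs to the equal-exclusion case. If exclusion is unequal or informative, the shift can be larger, smaller or opposite in sign. The main mixed model and the primary endpoint are not affected.

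**What to change.** In SAP Section 9.2.3, before unblinding:

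1. Delete the bullet that excludes patients above 20% missing, and the matching 20% condition that opens the imputation rules.
2. Keep all FAS patients and the existing worst-score rule for death and for hospital or ER periods.
3. Keep the higher-neighbour rule for isolated gaps, and say what counts as isolated.
4. Handle all other missing scores by delta-adjusted or reference-based multiple imputation. This includes gaps with no later score, for which the neighbour rule has only one side to work from. Ordinary imputation under missing at random would largely repeat the main model.
5. Report by arm the number of patients with more than 20% of questionnaires missing.

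The cost is SAP wording and slightly more analysis work, with no new data. The downside is more imputed values for poor responders, so the deltas or reference assumption should be fixed in advance and stated with the result.

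### The only named symptom-score sensitivity analysis gives no Day 28 value to patients who stop reporting, except for death or a stay covering Day 28, so missing-at-random is not stressed for ordinary dropout

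*SAP*

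**What the plan says.** All of this is in SAP Section 9.2.3 unless another section is named.

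- **Main analysis.** The overall score and each symptom score are compared over the period to Day 28 in a repeated-measures mixed model, "using a missing at random assumption for handling missing data". On missing values it states: "All available data will be used in the analysis; no imputation will be done for missing data".
- **Exclusion in the sensitivity analysis.** "Completely exclude from analysis any patients who are missing more than 20% of their required symptom score questionnaires", with an exemption: "unless the days where they are missing questionnaires fall after the patient experienced hospitalization, ER visit, or death".
- **Who is kept.** The lead-in to the imputation bullets covers patients at or below the 20% limit, and also those whose scores are missing because of an earlier hospitalization, ER visit or death.
- **Death.** "For any individual symptom scores that are missing because of the patient's prior death, impute the most severe possible answer".
- **Hospital or ER stay.** "If a patient has missing symptom scores during a period of hospitalization or ER visit, also impute the most severe possible answer".
- **Everything else.** "For patients missing scores for any other reason, the higher of the two surrounding scores will be imputed".
- **Overall score.** It is summed from reported or imputed items only where that can be done.

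The introduction to Section 9.2 uses a similar higher-score rule for the NIAID scale. There it is restricted to a missing assessment lying between two observed ones, and the text goes on to say what happens to scores that still cannot be imputed.

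**The concern.** A sensitivity analysis for a missing-at-random model should show whether the result survives if patients who stop reporting are doing worse than the model predicts. The final time point is where this matters most, because anyone who stops reporting for good is missing there.

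The catch-all rule needs a score before the gap and a score after it. A missing Day 28 score never has the second. With that rule unusable, the 20% exclusion and the mixed model decide what happens. Early dropouts leave the analysis, and late dropouts stay in with Day 28 missing, handled as in the main analysis. If the two analyses then agree, that would look like robustness, although the assumption about ordinary dropout at Day 28 had not been varied.

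There is also a practical problem. Section 14.1 requires independent double programming, and the text gives the two programmers no common instruction for a gap with no later score. They could carry the last score forward, leave it missing or extend the worst score, and these choices lead to different Day 28 data.

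**Working it through.** The SAP gives no figure of its own for this endpoint's missing data, so the check is mainly one of logic.

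**1. Can another assessment supply a later score?** The questionnaire analysis ends at Day 28. The Day 60 assessment (Section 11.1.2) records whether symptoms were present or absent over the prior 7 days. It does not use the 0-3 and 0-2 item scales, so it cannot serve as the second neighbour.

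**2. Event-free patients who stop reporting.** The number of required questionnaires is not in the SAP, so six schedules were assumed. Exclusion applies if missing ÷ required > 0.20.

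| Assumed schedule | Required | Most that may be missing | Last report: excluded | Last report: kept | Day 28 scored |
|---|---|---|---|---|---|
| Daily, Days 1-28 | 28 | 5 | Day 22 or earlier | Days 23-27 | none |
| Days 1-14, 21, 28 | 16 | 3 | Day 12 or earlier | Days 13, 14, 21 | none |
| Days 1-14, 28 | 15 | 3 | Day 11 or earlier | Days 12-14 | none |
| Days 1, 3, 5, 7, 14, 21, 28 | 7 | 1 | Day 14 or earlier | Day 21 | none |
| Baseline, 7, 14, 21, 28 | 5 | 1 | Day 14 or earlier | Day 21 | none |
| Baseline, 7, 14, 28 | 4 | 0 | all | none | none |

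For the daily schedule, 0.20 × 28 = 5.6, so at most 5 may be missing. A last report on Day 22 leaves 6/28 = 21.4% missing (excluded), and one on Day 23 leaves 5/28 = 17.9% (kept). The cut-off moves with the schedule; the last column does not.

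**3. Patients with an event.**
- Missing days follow death: worst score at Day 28, which is 12 × 3 + 2 × 2 = 40 on the overall score.
- In hospital or ER on Day 28: worst score.
- Discharged before Day 28, then stops reporting: the exemption speaks of days *after* the event and the lead-in of scores missing because of an *earlier* event, so the patient is kept. The worst-score bullet speaks of days *during* the stay, so post-discharge days fall to the catch-all rule, which lacks a second score. Section 9.1 tabulates stays under 24 hours, so *during* may cover as little as one day.

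**4. Ceiling on the discharged group.** Section 4.1 assumes 10% and 3% event rates in unvaccinated patients and none in vaccinated patients. With 20% vaccinated, 0.80 × 10% = 8.0% and 0.80 × 3% = 2.4%, which reproduces the SAP's overall rates. With 250 per arm, 0.080 × 250 = 20 placebo and 0.024 × 250 = 6 sargramostim patients. These are all expected primary events, including deaths and patients who resume reporting, so they are upper bounds for the discharged group who stop reporting.

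**5. Illustrative size.** Assumed inputs: 5-15% missing at Day 28, missing sargramostim patients 1-4 points worse than modelled, SD of 5.
- Shift in treatment difference = share × penalty: from 0.05 × 1 = 0.05 to 0.15 × 4 = 0.60 points.
- SE = 5 × √(2 / (250 × (1 − share))): 0.46 at 5% missing and 0.49 at 15%.
- Ratio: 0.05 / 0.46 ≈ 0.1 to 0.60 / 0.49 ≈ 1.2 standard errors.

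**The case against.** A reader might infer that nobody who stops reporting receives a Day 28 value, or that missing-at-random is never tested there. The documents do not support this. Scores missing after death, or during a stay that covers Day 28, are set to the worst answer, which is a real departure from missing-at-random for the patients with the worst outcomes.

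Other points on the plan's side:

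- Section 4.5 allows further missing-data rules before unblinding, Section 5.3 places decisions on missing data and final imputation in the blinded review, and Section 12.2 allows extra robustness analyses. This stands as a route to a correction, but none of the three fixes a rule for a gap with no later score.
- The post-discharge reading is not certain. The lead-in could be taken to mean that post-event days should also get the worst score. What stands is that the exemption, lead-in and bullet disagree, and only the literal reading leaves these patients unscored.
- The numerical shift rests wholly on assumed inputs, and 0.1 to 1.2 standard errors runs from negligible to notable. That is fair.
- The rule works for gaps with scores on both sides, so the planned Day 7 and Day 14 estimates are less affected. The mixed model still uses kept patients' earlier scores. The primary endpoint is untouched.
- The 20% exclusion can be criticised in its own right. It matters here only because it removes early dropouts; lifting it would still leave their Day 28 scores without a second neighbour.
- A one-sentence fallback would make the rule computable. It would, however, show the result under one fixed assumption, not how far that assumption can be pushed.

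**Conclusion.** The point holds in a bounded form. For patients who stop reporting for reasons other than death or a hospital or ER stay covering Day 28, the only sensitivity analysis named for this secondary endpoint supplies no Day 28 value. Those above the 20% limit without a prior event are excluded, those at or below it have no second neighbouring score, and those discharged after an event are, on the literal text, kept but unscored. Missing-at-random is therefore not stressed for ordinary dropout at Day 28.

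This conclusion comes from the text and was the same under all six assumed schedules. Its numerical importance cannot be established from the SAP: the 20 and 6 event patients are ceilings for one subgroup, and the 0.05-0.60 point shift is an illustration. The matter should be corrected before unblinding. It does not threaten the primary analysis.

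**What to change.** In Section 9.2.3:

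1. Limit the higher-of-two-scores rule to gaps with an observed score on both sides, as Section 9.2 already does for the NIAID scale.
2. For scores with no later observation, use multiple imputation under the mixed model, then add a range of penalties to the imputed sargramostim scores (for example 0, 1, 2, 3 and 4 points on the overall score). Report the penalty at which the Day 28 conclusion changes.
3. Make the exemption, the lead-in and the worst-score bullet refer to the same days, so that post-discharge days have one stated handling.

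The cost is SAP wording and modest programming before unblinding, with no new data or patients. The result becomes a range instead of one number.
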